Medical and scientific judgement should be exercised in deciding whether other situations should be considered serious reactions, such as important medical events that might not be immediately life threatening or result in death or hospitalisation but might jeopardise the patient or might require intervention to prevent one of the other outcomes listed above. Examples of such events are intensive treatment in an emergency room or at home for allergic bronchospasm, blood dyscrasias or convulsions that do not result in hospitalisation or development of dependency or abuse. Any suspected transmission via a medicinal product of an infectious agent is also considered a serious adverse reaction.

AEs considered 'Always Serious'

In accordance with the European Medicines Agency initiative on Important Medical Events, Boehringer Ingelheim has set up a list of further AEs which, by their nature, can always be considered to be 'serious' even though they may not have met the criteria of an SAE as given above.

The latest list of 'Always Serious AEs' can be found in the RDC system, a remote data capture system which allows the entry of trial data at the trial site. These events should always be reported as SAEs as described above.

Cancers of new histology and exacerbations of existing cancer must be reported as a serious event regardless of the duration between discontinuation of the drug and the occurrence of the cancer.

Adverse events of special interest (AESIs)

The term AESI relates to any specific AE that has been identified at the project level as being of particular concern for prospective safety monitoring and safety assessment within this trial, e.g. the potential for AEs based on knowledge from other compounds in the same class. AESI need to be reported to the sponsor's Pharmacovigilance Department within the same timeframe that applies to SAE, see [Section 5.5.2.2](#).

Proprietary confidential information © 2016 Boehringer Ingelheim International GmbH or one or more of its affiliated companies

The following are considered as AESIs in this trial:

Hepatic injury, as defined by the following alterations of hepatic laboratory parameters:

- An elevation of AST and/or ALT ≥ 3 -fold ULN combined with an elevation of total bilirubin ≥ 2 -fold ULN measured in the same blood sample, and/or
- Marked peak aminotransferase (ALT, and/or AST) elevations ≥ 10 fold ULN

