[REDACTED] (see [Section 2.1](#)), a preliminary REP is defined as [REDACTED] after administration of BI 1467335. Therefore, all AEs which will occur throughout the treatment phases and the preliminary REP will be considered as 'on treatment' (see [Section 7.3.3](#)). Events which occur after the preliminary REP and prior to the next drug administration will be considered as 'follow-up' events.

AE reporting to sponsor and reporting timelines

The Investigator must report SAEs, AESIs, and non-serious AEs which are relevant for the reported SAE or AESI, on the BI SAE form via fax immediately, within 24 hours of awareness, to the sponsor's unique entry point (country specific contact details will be provided in the ISF). The same timeline applies if follow-up information becomes available. On specific occasions the Investigator could inform the sponsor upfront via telephone. This does not replace the requirement to complete and fax the BI SAE form.

With receipt of any further information to these events, a follow-up SAE form has to be provided. For follow-up information, the same rules and timelines apply as for the initial information.

Information required

For each AE, the investigator should provide the information requested on appropriate CRF pages and the BI SAE form (if applicable).

The investigator should determine the causal relationship to the trial medication.

The following should also be recorded as an (S)AE in the CRF and on the SAE form (if applicable):

- Worsening of the underlying disease or of other pre-existing conditions

Proprietary confidential information © 2016 Boehringer Ingelheim International GmbH or one or more of its affiliated companies

- Changes in vital signs, ECG, physical examination and laboratory test results, if they are judged clinically relevant by the investigator

If such abnormalities have already pre-existed prior to trial inclusion, they will be considered as baseline conditions.

All (S)AEs, including those persisting after the individual subject's end of trial, must be followed up until they have been resolved, sufficiently characterised, or no further information can be obtained.

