6.2.3 End of trial examination

For AE assessment, laboratory tests, body weight, recordings of ECG and vital signs, and physical examination during the end of trial period, see [Sections 5.2.2](#) to [5.2.5](#).

Subjects who discontinue treatment before the end of the planned treatment period should undergo the end of trial visit.

All abnormal values (including laboratory parameters) that are judged clinically relevant by the investigator will be monitored using the appropriate tests until a return to a medically acceptable level is achieved. (S)AEs persisting after subject's end of trial must be followed up until they have resolved, have been sufficiently characterised, or no further information can be obtained.

The end of the trial as a whole is defined by the 'last regular visit completed by last subject' or 'end date of the last open AE' or 'date of the last follow-up test' or 'date of an AE has been decided as sufficiently followed-up', whichever is latest.

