7.3.3 Safety analyses

Safety will be assessed for the endpoints listed in [Section 5.2.1](#). All treated subjects (i.e., all subjects who received at least one dose of study drug), will be included in the safety analysis. Safety analyses will be descriptive and will be based on BI standards. No hypothesis testing is planned.

The analyses will be done by ‘treatment at onset’.

Treatments will be compared in a descriptive way. Tabulations of frequencies/proportions will be used for the evaluation of categorical (qualitative) data, and tabulations of descriptive statistics will be used to analyse continuous (quantitative) data.

Measurements (such as ECG, vital signs, or laboratory parameters) or AEs will be assigned to treatments (see [Section 4.1](#)) based on the actual treatment at the planned time of the measurement or on the recorded time of AE onset (concept of ‘treatment emergent AEs’).

Proprietary confidential information © 2016 Boehringer Ingelheim International GmbH or one or more of its affiliated companies

Therefore, all AEs which will occur throughout the treatment phase and the preliminary REP will be considered as 'on treatment'. Events which occurred after the preliminary REP will be considered as 'follow-up' events (refer to [Section 5.2.2.2](#)).

These assignments, including the corresponding time intervals, will be defined in detail in the TSAP.

Adverse events will be coded using the Medical Dictionary for Regulatory Activities (MedDRA). Frequency, severity and causal relationship of AEs will be tabulated by treatment, primary system organ class and preferred term. SAEs and other significant AEs (according to ICH E3), and AESIs will be listed separately (see [Section 5.2.2.1](#)).

Laboratory data will be compared to their reference ranges. Values outside the reference range as well as values defined as clinically relevant will be highlighted in the listings. Additionally, differences from baseline will be evaluated.

Vital signs or other safety-relevant data observed at screening, baseline, during the course of the trial and at the end-of-trial evaluation will be assessed with regard to possible changes compared to findings before start of treatment.

Relevant ECG findings will be reported as AEs.

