#### **7.8.2      Laboratory data**

**CTP (Section 7.3.3 Safety analyses):** *Laboratory data will be compared to their reference ranges. Values outside the reference range as well as values defined as clinically relevant will be highlighted in the listings. Additionally, differences from baseline will be evaluated.*

The analyses of laboratory data will be based on BI standards (6). Descriptive statistics of laboratory values over time and for the difference from baseline will be provided. Frequency tables of changes between baseline and last value on treatment with respect to the reference range will be presented.

Possibly clinically significant abnormal laboratory values are only those identified either in the Investigator's comments on the database or at the RPM/DBLM at the latest. It is the investigator's responsibility to decide whether a lab value is clinically significant abnormal or not. Standard or project-specific rules for flagging clinically significant values will not be applied in this study. Possibly clinically significant abnormal laboratory values will only be presented within the scope of the listing of investigator comments.

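### The only laboratory shift table uses the last on-treatment value with no rule for repeats, so a resolved out-of-range excursion can drop out of the by-treatment counts

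*SAP*

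**What the plan says.** SAP 7.8.2 plans two summaries. One is by time point: "Descriptive statistics of laboratory values over time and for the difference from baseline will be provided". The other is the shift table: "Frequency tables of changes between baseline and last value on treatment with respect to the reference range will be presented". No other laboratory shift table is described.

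On flags, the same section says: "Standard or project-specific rules for flagging clinically significant values will not be applied in this study". It adds: "Possibly clinically significant abnormal laboratory values will only be presented within the scope of the listing of investigator comments". At its head it reproduces protocol 7.3.3: "Values outside the reference range as well as values defined as clinically relevant will be highlighted in the listings".

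SAP 6.7 says how repeated laboratory values count for baseline (the last repetition before dosing in the period). It has no matching statement for repeats after dosing. SAP Table 6.1: 2 ends the on-treatment phase at dosing plus the REP, whose length is redacted.

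Protocol 6.2.3 states that abnormal values judged clinically relevant by the investigator "will be monitored using the appropriate tests until a return to a medically acceptable level is achieved". Protocol 5.2.3 allows retests, which need not be fasting. Protocol 5.2.2.2 lists among the findings to be recorded as adverse events: "Changes in vital signs, ECG, physical examination and laboratory test results, if they are judged clinically relevant by the investigator".

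**The concern.** A last-value rule and a follow-until-recovery rule pull in opposite directions. If a subject has an abnormal result and is retested, the later result is the one more likely to be back in range. If it counts as the last value, the table shows no shift for a subject who had one. A subject with no abnormality usually has no retest, so the rule bites mainly where there was something to see.

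Protocol 2.3 relies on laboratory monitoring for signs of reduced immune response and asks for timely detection of liver test changes. These are the parameters for which a reader would want to know how many subjects per treatment left the reference range at any time on treatment. The planned shift table is the only summary that gives such a count, and it may give it only for the final sample.

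A second, smaller matter lies in the same section. The SAP confines possibly clinically significant values to the listing of investigator comments, while the protocol sentence it reproduces has clinically relevant values highlighted in the listings. SAP section 4 declares all analyses to be in accordance with the protocol.

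**Working it through.** The plan states no figure to reproduce. The check asks when the last and the worst on-treatment values can differ, and by how much.

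**Inputs**
- 18 subjects, each receiving all three treatments (protocol synopsis and 3.1).
- Scheduled safety laboratory samples (Flow Chart): screening; Day -5 to -1 before periods 2 and 3; 24 h after each dose; end of trial on Day 22 to 29. The chart's columns are broken in the text available, so the 24 h entry is a reading of it.
- Minimum washout of 21 days = 504 h between doses.
- REP: redacted, so treated as an assumption and varied from 1 to 28 days.

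**Step 1: general relation.** The last value is one of the on-treatment values. If the last value is out of range, so is the minimum or the maximum. Hence, for each parameter and treatment:

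subjects out of range by last value ≤ subjects out of range by worst value.

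The difference is the number of subjects with an out-of-range value on treatment followed by an in-range last value. With one on-treatment value per subject, the difference is zero.

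**Step 2: scheduled samples inside the phase.**
- 24 h sample: day 1 after dosing.
- Visit 3/4 sample, at the minimum washout: (504 − 123)/24 = 15.9 days to (504 − 12)/24 = 20.5 days after the previous dose.
- End-of-trial sample: 22 − 1 = 21 to 29 − 1 = 28 days after the third dose.

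| Assumed REP | Scheduled on-treatment samples, periods 1 and 2 | Period 3 |
|---|---|---|
| just over 1 to about 15.9 days | 24 h only | 24 h only |
| about 16 to 20.5 days | 24 h, and Visit 3/4 sample if taken early enough | 24 h only |
| above 20.5, up to 21 days | 24 h and Visit 3/4 sample | 24 h only |
| above 21 days | 24 h and Visit 3/4 sample | 24 h, possibly end of trial |

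**Step 3: consequence.**
- REP up to about 15.9 days: the 24 h value is normally both last and worst, and an excursion at 24 h is tabulated as a shift. It disappears only if an unscheduled repeat (i) falls inside the phase, (ii) counts as the last value and (iii) is within the reference range.
- REP of about 16 days or longer: in periods 1 and 2 the Visit 3/4 sample can become the last value with no repeat at all. A 24 h excursion that has resolved by then is not counted. That sample is also the natural baseline for the next period under SAP 6.7.

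**Step 4: size.** Let k of 18 subjects go from in range at baseline to out of range at 24 h, all with an in-range later value that counts as last.

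| k | Last-value table | Worst-value table |
|---|---|---|
| 1 | 0/18 | 1/18 = 5.6% |
| 2 | 0/18 | 2/18 = 11.1% |
| 3 | 0/18 | 3/18 = 16.7% |

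If no later value falls inside the phase, both tables show k. The documents give no basis for estimating how often either case would occur.

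**The case against.** The strongest reply is that the mechanism limits its own harm. The follow-up rule in protocol 6.2.3 covers only values judged clinically relevant, and those must also be recorded as adverse events, which SAP 7.8.1 tabulates by treatment and by maximum intensity. The end point of follow-up is medical acceptability, not the reference range, so a final repeat may still show as a shift. The sponsor's laboratory standard cited in SAP 7.8.2 may settle how repeats count. Every out-of-range value stays highlighted in the listings, and the by-time summaries include minimum and maximum (SAP 7). Safety is descriptive in a single-dose study in healthy men.

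Most of this stands and narrows the point. What remains is chiefly an excursion that resolves without being judged clinically relevant. Listings and minimum or maximum values show that it occurred, but do not give the number of subjects per treatment who moved out of range.

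A reader might also infer that SAP 7.8.2 switches off the hepatic criteria. It does not. The protocol's definition ("Hepatic injury, as defined by the following alterations of hepatic laboratory parameters") is repeated in SAP 7.8.1 with its own table and listing, and the sentence on rules concerns flags for clinical significance only. Nor does protocol 7.3.3 require clinical relevance to be set by algorithm; both documents leave it to the investigator. The inconsistency is confined to where such values are displayed. The two documents describe no programmed comparison of laboratory data with reported hepatic events, but one may exist in the data management plan named in protocol 8.2.

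**Conclusion.** The point holds in a limited form. The planned shift table can only equal or undercount a worst-value table, and the SAP text leaves open whether on-treatment repeats count. The undercount is zero when the 24 h value is the only on-treatment value. It is one subject (5.6 percentage points of 18) for each resolved excursion followed by an in-range last value inside the phase. This rests on the Flow Chart as read, the minimum 21-day washout and an unknown REP.

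Two stronger readings are tempting: that any resolved liver or blood-count excursion will be tabulated as no shift, and that it will vanish from the report. The documents support neither. The first depends on the conditions in Step 3, and the second is contradicted by the listings, the by-time statistics and the adverse event tables. The primary PK analysis and the sample size are unaffected.

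**What to change.** In SAP 7.8.2:

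1. Base the shift tables on the worst on-treatment value: period baseline against the lowest and against the highest value in the on-treatment phase, counting unscheduled repeats. Keep the last on-treatment value as an additional column and state whether repeats count for it.
2. Reconcile the sentence confining possibly clinically significant values to the listing of investigator comments with the reproduced protocol 7.3.3 text, so that it is clear where investigator-judged values are highlighted.
3. Optionally, add a programmed check of the two existing hepatic criteria against the listing of adverse events of special interest before database lock, unless the data management plan already has one.

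The cost is a few lines of SAP text and minor programming on laboratory data that will already be loaded. The drawback is that a worst-value table will show a few more isolated shifts of no clinical importance; the last-value column lets the reader see which had resolved.

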#### **7.8.3      Vital signs**

**CTP (Section 7.3.3 Safety analyses):** *Vital signs or other safety-relevant data observed at screening, baseline, during the course of the trial and at the end-of-trial evaluation will be assessed with regard to possible changes compared to findings before start of treatment.*

Only descriptive statistic of vital signs over time and for the difference from baseline are planned for this section of the report.

Clinically relevant findings in vital signs data will be reported as AEs and will be analysed as part of the AE analysis.

#### **7.8.4      ECG**

**CTP (Section 7.3.3 Safety analyses):** *Relevant ECG findings will be reported as AEs.*

No separate listing or tables will be prepared.

[figure not shown]
## **7.8.5      Others**

### **7.8.5.1    Physical examination**

Physical examination findings will be reported as relevant medical history/baseline condition (i.e., a condition already existent before intake of study drug) or as AE and will be summarised as such. No separate listing or analysis of physical examination findings will be prepared.

## **10. HISTORY TABLE**

Table 10: 1 History table

Version	Date (DD-MMM-YY)	Author	Sections changed	Brief description of change
Final	15-MAY-2017	[REDACTED]	None	This is the final TSAP without any modification.
